1 SUMMARY

1.1 TITLE

A Single Center, Randomized, Open-Label, Two Arm, Crossover, Study of Subject Productivity Improvement and Satisfaction with Migraine Treatment Using Treximet™ vs Usual Triptan. “Does Treximet™ Improve Productivity and Patient Satisfaction Due to Sustained Response and Consistency of Response?”
V 08-26-15

1.2 RATIONALE

The finding that triptan + Nonsteroidal Anti-inflammatory (NSAID) as a combination in the acute treatment of migraine is superior to either of the medications alone suggests that there should be pharmcoeconomic consequences to appropriate combination treatment. In addition, patient satisfaction should correlate to more effective treatment. Accordingly, we have sought and received a grant to evaluate work productivity, patient satisfaction, and effectiveness of treatment in comparing sumatriptan + naproxen sodium to triptan monotherapy in patients in the work place.

2 OBJECTIVES

Specific Aim 1: To compare work productivity as measured by the Work Productivity Assessment Instrument (WPAI) after each of the 3 attacks treated with usual triptan monotherapy to each of the 3 attacks treated with Treximet.

Specific Aim 2: After 3 attacks treated with usual triptan monotherapy, and after 3 attacks treated with Treximet, to compare the Completeness of Response Survey (CORS), which will be collected and tabulated.

Specific Aim 3: To compare Migraine-ACT after usual triptan monotherapy, and Migraine-ACT after Treximet. Migraine-ACT is a validated patient-derived instrument for measuring effectiveness of acute treatment, and is particularly suited to evaluating this hypothesis because of its items on consistency of response, comfort level with treatment for planning activities, and functional evaluation:

- Consistency of response: *Does your migraine medication work consistently, in the majority of your attacks?*
- Global assessment of relief: *Does the headache pain disappear within 2 hours?*
- Impact: *Are you able to function normally within 2 hours?*
- Emotional response: *Are you comfortable enough with your medication to be able to plan your daily activities?*

Specific Aim 4: To determine if there is an interaction between medication (usual triptan vs Treximet) and patient reported pain at time of dose with respect to workplace productivity as measured by the WPAI — is one medication more effective at improving workplace productivity when migraines are more severe at time of dose?

Specific Aim 5: To compare various self-reported aspects of patient health acquired in the Knowledge Program (KP) after 3 treatments with usual triptan and 3 treatments with Treximet.

3 INVESTIGATIONAL PLAN

3.1 SUMMARY OF STUDY DESIGN

This is a single site, randomized, open-label, two arm, crossover, study of subject productivity improvement and satisfaction with migraine treatment using Treximet™ vs usual triptan.

This study will recruit 60 patients who are employed in a paying job, who have episodic migraine (<15 days/month), who are using acute care triptan monotherapy for their migraine (excluding combinations of any sort, such as acetaminophen [APAP] and non-steroidals [NSAIDs]) and who have no contraindications to triptan or NSAID use.

In one arm of the study, patients will treat 3 work day migraines with their usual triptan and in the other arm of the study the same patients will treat 3 work day migraines with Treximet. The medication that they use in the first arm of the study is determined by randomization. They will maintain headache diaries for the duration of the study and fill out the WPAI after each work day migraine. After treating 3 work day migraines, they will also fill out CORS Part 1 and Migraine-ACT.

Between the completion of the 3rd migraine attack treatment, and the start of the second treatment arm, there will be a minimum of a 48 hour washout period and an office visit.

In the second arm, after cross over to the other treatment, the sixty patients will maintain headache diaries, treat 3 attacks during any day in which they are scheduled to work, and fill out the WPAI after each attack. Additionally, after 3 attacks are treated, they will fill out CORS Part 1, CORS Part 2 and Migraine-ACT. This second arm differs from arm one in that the subjects will treat their migraines with the other medication from that assigned in the first arm.

Subject participation will last approximately 3 months, depending on the days needed to treat migraines during the workday according to protocol.

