6 STUDY ASSESSMENTS

The Study Flowsheet (time and events table) provided below lists the study activities throughout the protocol.

STUDY FLOW CHART			
		Washo	

	Screen (Office Visit)	First Arm (Treximet™ or Usual Triptan) - Treat 3 Migraines			ut Windo w (at least 48h post V4 tx) (Office Visit)	Second Arm (Treximet™ or Usual Triptan) - Treat 3 Migraines			EOS (Office Visit)
Procedure	Visit 1	Visit 2	Visit 3	Visit 4	Visit 5	Visit 6	Visit 7	Visit 8	Visit 9
Informed Consent	X								
Inclusion/Exclusion	X								
Office Visit (PE, Vitals Neuro Exam)	X								X
Urine Pregnancy Test (if female and childbearing potential)	X				X				X
Conmeds	X				X				X
AE/SAE collect					X				X
Migraine History & update	X				X				
Medical History- & update	X				X				X
Educ/Disp/Revu Diary	X	X	X	X	Collect	x	x	x	Collect
Randomization	X				Switch TX Arm				
Disp/Take/Collect Study Drug	X	X	X	X	Collect	X	X	X	Collect
WPAI		X	X	X	Collect	X	X	X	Collect
CORS 1				X	Collect			X	Collect
CORS 2								X	Collect
MigraineAct	X			X	Collect			X	Collect
KP Data	X				X				X

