6.1 EFFICACY

Efficacy comparisons of Treximet™ vs Usual Triptan treatment will be collected using the CORS 1, CORS 2, WPAI and Migraine-Act assessment tools. Pain level at time of dose is captured as part of the Study Diary.

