For the secondary outcome Migraine-ACT, a binary outcome will be calculated (e.g. 0=if Migraine-ACT is not favorable, 1=if Migraine-ACT is favorable) and used to identify carryover. [Note: A favorable response in Migraine-ACT is a value of 3 or 4.] The odds of a favorable triptan f/b Treximet sequence will be compared to the odds of a favorable Treximet f/b triptan sequence through an odds ratio, which will be evaluated with a chi-square test (see Toutenburg¹ p. 369). If no significance is found, then the assumption will be that there is no carryover effect. That assumption will be applied when analyzing both the binary and ordinal (levels > 2) values of Migraine-ACT. Treatment differences will be evaluated through a generalized estimating equation with a logit link function (or cumulative logit link function). The models will include trial period, sequence, and treatment as fixed effects. If carryover does exist, then only first trial period results will be used. In that case, treatment differences will be evaluated through a chi-squared test for binary outcomes and through a Mann-Whitney U-test for ordinal outcomes (levels > 2).

All tests for significance will be conducted at the 95% confidence level (i.e. $\alpha = .05$). Analysis will be conducted in SAS® v9.2.

CORS data will be tabulated as follows: For CORS part 1, a frequency count and percent by question answer will be provided. This will be reported by treatment (Treximet™ vs triptan) within period and in total. For CORS part 2, a frequency count and percent will be provided by answer for each question. In addition, a de-identified data set containing CORS information will be provided to Pernix Therapeutics for additional psychometric analysis.

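### On-treatment Migraine-ACT and CORS 1 are scheduled only after the third treated attack in each period, so no rating is provided for a patient who stops that period's treatment sooner

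*Combined protocol and SAP*

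**What the plan says.** Section 3.1 sets the timing for the first arm, "After treating 3 work day migraines, they will also fill out CORS Part 1 and Migraine-ACT", and for the second, "Additionally, after 3 attacks are treated, they will fill out CORS Part 1, CORS Part 2 and Migraine-ACT". Aim 2 in section 2 likewise defines the CORS comparison after three attacks on each treatment.

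The flow chart in section 6 matches. CORS 1 is marked at Visits 4 and 8, and Migraine-ACT at Visits 1, 4 and 8. At the office visits that close each period (Visits 5 and 9) both forms are only collected. There is no column for early termination.

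The crossover is described only for a patient who has finished three attacks: the washout and office visit fall "Between the completion of the 3rd migraine attack treatment, and the start of the second treatment arm".

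Section 2 gives Migraine-ACT its role: "Migraine-ACT is a validated patient-derived instrument for measuring effectiveness of acute treatment". Section 8.2 turns it into a binary outcome ("A favorable response in Migraine-ACT is a value of 3 or 4") and also analyses it as ordinal, using generalized estimating equations (GEE). CORS is tabulated by treatment. Section 8.2 defines no analysis population and no rule for a missing Migraine-ACT or CORS rating.

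**The concern.** A patient who treats one attack, gets no relief or has an adverse reaction, and will not use the drug again does not reach Visit 4 or Visit 8. The plan then provides no Migraine-ACT or CORS 1 for that drug, although this patient is among the most likely to rate it poorly. If it happens in the first period, no route into the second is described, so a rating of the other drug may be lost as well.

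Early stopping is plausible from the documents themselves. Treatment is open label. Patients enter on a triptan they already use, while Treximet may be new to them. The appended label advises reconsidering the diagnosis before further Treximet use when the first treated attack does not respond.

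At stake are Aims 2 and 3, and the satisfaction question in the study title. A rating that was never taken cannot be recovered in the analysis.

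**Working it through.** **The plan's own figure.** The only figure stated for the design is 86% power for WPAI. With a difference of 1, an SD of the difference of 2.5, N = 60 and two-sided alpha 0.05 (sidedness assumed), the standard error is 2.5/√60 = 0.323. The noncentral t with 58 degrees of freedom gives 86.1%, so the figure reproduces. It does not bear on Migraine-ACT or CORS, for which the plan states no expected rates and no power.

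**What is collected under treatment if a patient stops after one or two attacks**

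| Measure | Planned timing | Available for that drug? |
|---|---|---|
| WPAI | after each treated attack | yes, for the attacks treated |
| Diary pain at dose | daily diary | yes |
| CORS 1 | third attack (Visits 4, 8) | not provided for |
| Migraine-ACT | third attack (Visits 4, 8) | not provided for |

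Migraine-ACT at Visit 1 presumably describes the usual triptan before study treatment. Treximet has no counterpart to it.

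**Effect on the favourable rate (all inputs assumed).** Let p be the true favourable rate among all who start a drug, s the share who stop early, and f the share of those stoppers who would have rated it favourably. The rate seen among three-attack completers is

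(p − s·f) / (1 − s).

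If stoppers resemble everyone else (f = p), this equals p and there is no bias. If all stop as failures (f = 0), it is p/(1 − s), the upper end of the illustration. With p = 60% on both drugs and f = 0:

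| Stopping, drug A vs B | Completer rates, A vs B | Spurious difference favouring B |
|---|---|---|
| 0% vs 10% | 60.0% vs 0.60/0.90 = 66.7% | 6.7 points |
| 5% vs 15% | 0.60/0.95 = 63.2% vs 0.60/0.85 = 70.6% | 7.4 points |
| 0% vs 20% | 60.0% vs 0.60/0.80 = 75.0% | 15.0 points |
| 10% vs 10% | 66.7% vs 66.7% | 0 (both inflated by 6.7) |

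For 0% versus 10%, varying p from 40% to 70% moves the difference from 4.4 points (0.40/0.90 = 44.4%) to 7.8 points (0.70/0.90 = 77.8%).

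In counts, if all 60 start both drugs, 36 would be favourable on each. With six stopping B as failures, the completer rates are 36/60 = 60.0% and 36/54 = 66.7%.

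**The same effect seen from the completer side.** Suppose completers show 60% on both drugs. Counting stoppers as not favourable, 5% versus 10% stopping gives 0.95 × 60% = 57% versus 0.90 × 60% = 54%, so 3 points are hidden. With 0% versus 15% it is 60% versus 0.85 × 60% = 51%, so 9 points are hidden.

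**Direction.** The label's adult trials show no 2-hour relief in 35% and 43% on Treximet (100 − 65, 100 − 57) and in 45% and 50% on sumatriptan alone (100 − 55, 100 − 50). These are single-attack response rates, not stopping rates, and the usual-triptan patients here have already accepted their drug. The documents therefore do not settle which drug would be stopped more often.

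**The case against.** The strongest defence is that the timing follows from the instruments. Migraine-ACT asks about consistency across most attacks, and CORS asks how often one dose gives complete relief. Neither question means much after a single attack, and consistency of response is central to the hypothesis. This stands. It is a reason to keep the third attack as the default and to show the three-attack result. It is not a reason to have no rating at all from a patient who has abandoned the drug.

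Other points also stand:

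- Each period needs only three attacks, and a second dose or usual rescue is allowed from 2 hours, which may limit stopping.
- Some patients may fall short simply because too few migraines occur on work days.
- CORS is only tabulated, and its counts would show missing ratings.
- Migraine-ACT is secondary.
- Scoring stoppers as not favourable is one of several defensible estimands. It needs a recorded reason, and in an open-label trial that attribution is itself open to bias.

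A reader might infer that effectiveness as a whole is measured in completers only. The documents do not support that. Section 6.1 says efficacy data "will be collected using the CORS 1, CORS 2, WPAI and Migraine-Act assessment tools", and WPAI, the primary outcome, is completed after every attack and has a sensitivity model using all three. Section 8.2 does not say whether the last attack means the third or the last one treated, but the data would exist either way.

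A reader might also infer that early stoppers can never rate the drug, or that only patients who finish both arms are analysed. The first is read from silence, since nothing forbids a rating at an office visit. The second is not stated, since the GEE can use a single period's rating.

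**Conclusion.** The gap is real but limited to on-treatment Migraine-ACT and CORS 1. Followed as written, the plan compares ratings only from patients who treated three attacks with the drug in question. Unequal stopping for failure or intolerance would favour the drug stopped more often.

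The size cannot be derived from the documents. The 6.7-point figure assumes a true favourable rate of 60% on both drugs, 0% versus 10% stopping, and that every stopper would have rated the drug unfavourably. With equal stopping the difference between drugs is unbiased under these assumptions, although both rates are inflated. It would be too strong to say that the design favours Treximet: the direction depends on stopping rates that the documents do not give.

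**What to change.** In section 3.1 and the flow chart, have every patient who treated at least one attack in a period complete CORS 1 and Migraine-ACT after the third attack or, if earlier, when treatment in that period ends, at the latest at that period's office visit (Visit 5 or 9). Record the number of attacks treated and the reason for stopping.

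In section 8.2:

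- Analyse all available ratings in both the binary and the ordinal Migraine-ACT models, and tabulate CORS on the same basis.
- Show the three-attack completer result beside it.
- Add a sensitivity analysis of the binary outcome in which a patient who stopped for lack of effect or intolerance and has no score counts as not favourable.

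The forms and visits already exist, so the cost is a wording change in 3.1, a flow chart edit, a short addition to 8.2, and data fields for the number of attacks and the reason for stopping. The downside is that some ratings will rest on one or two attacks, which limits the consistency and frequency items. The completer display lets the reader see how much that matters.

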4. SUBJECT SELECTION

4.1 NUMBER OF SUBJECTS

This study will enroll 60 subjects for participation. There are no other sites for this study.

The sample size was chosen to be a sufficient number to assess the effect of Treximet on the WPAI using a crossover design in which patients will serve as their own controls.

Based on previous GSK studies on Treximet utilizing the WPAI, the effect size between Treximet and usual triptan care is expected to be small. In those studies, comparisons of Treximet to placebo yielded differences of 0.4 to 1.4. For this study, a one-point WPAI difference between Treximet and triptan is assumed to be clinically meaningful. Furthermore, the GSK Treximet studies were parallel designs with standard deviations ranging from 2.5 to 3.5. To account for the correlation from patients acting as their own controls in this crossover design, a standard deviation of the difference equal to 2.5 is assumed. Under these assumptions, a total sample of 60, with 30 in each sequence, would power the study at 86%.

4.2 INCLUSION CRITERIA:

A subject will be eligible to participate in this study if all of the following criteria apply:

1. subject is 18 years or older at screening
2. subject has a history of migraine greater than 1 year
3. subject has been diagnosed with migraine before age 50
4. subject is an employed person (is paid wages for his/her work)

5. subject has diagnosis of episodic migraine, by IHS criteria
6. subject uses triptan monotherapy as the primary migraine abortive treatment
7. subject is not pregnant or nursing

4.3 EXCLUSION CRITERIA:

A subject will not be eligible to participate in this study if any of the following criteria apply:

1. subject is less than 18 years of age at screening
2. subject does not have history of migraine greater than 1 year
3. subject was diagnosed with migraine after age 50
4. subject is not currently employed
5. subject does not have diagnosis of episodic migraine
6. subject does not use triptan monotherapy as primary migraine abortive treatment
7. subject is pregnant or nursing
8. subjects with a history of stroke, myocardial infarction (including vasospastic coronary artery disease [CAD] or cardiovascular thrombotic events)
9. subjects with gastrointestinal disease history to include ulcers, bleeding or perforations of the stomach or intestines
10. subjects with a history of significant renal or hepatic disease.
11. subjects with a history of significant ischemic cardiac symptoms (to include angina pectoris of any type; silent myocardial ischemia; cerebrovascular disease (including any type of stroke, transient ischemic attack), or peripheral vascular disease; such as ischemic bowel disease; coronary artery bypass graft surgery)
12. subjects with uncontrolled hypertension
13. subjects with use of monoamine oxidase-A inhibitors
14. subjects with current use of ergotamine-containing or ergot-type medications, like DHE
15. subjects using 5-HT agonists
16. subjects with diagnosis of basilar or hemiplegic migraines
17. subjects with allergy to naproxen
18. subjects who are allergic to aspirin or NSAIDS where such allergies induce syndrome of asthma, nasal polyps, urticaria and hypotension

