- Wolff-Parkinson-White syndrome or other cardiac accessory conduction pathway disorders. (4)
- History of stroke, transient ischemic attack, or hemiplegic or basilar migraine. (4)
- Peripheral vascular disease. (4)
- Ischemic bowel disease. (4)
- Uncontrolled hypertension. (4)

FULL PRESCRIBING INFORMATION: CONTENTS*

- 1 INDICATIONS AND USAGE
- 2 DOSAGE AND ADMINISTRATION
 - 2.1 Dosage in Adults
 - 2.2 Dosage in Pediatric Patients 12 to 17 years of age
 - 2.3 Dosage in Patients with Hepatic Impairment
 - 2.4 Administration Information
- 3 DOSAGE FORMS AND STRENGTHS
- 4 CONTRAINDICATIONS
- 5 WARNINGS AND PRECAUTIONS
 - 5.1 Myocardial Ischemia, Myocardial Infarction, Stroke, Prinzmetal's Angina
 - 5.2 Gastrointestinal Bleeding, Ulceration, and Perforation

- Recent (within 24 hours) use of another 5-HT₁ agonist (e.g., another triptan) or of ergotamine-containing medication. (4)
- Concurrent or recent (past 2 weeks) use of monoamine oxidase-A inhibitor. (4)
- Asthma, rhinitis, and nasal polyps syndrome induced by aspirin or other NSAID/analgesic drugs. (4)
- Hypersensitivity to sumatriptan, naproxen, or any other component of TREXIMET (angioedema and anaphylaxis seen). (4)
- Third trimester of pregnancy. (4)
- Severe hepatic impairment. (4)

WARNINGS and PRECAUTIONS

- Myocardial ischemia/infarction, stroke, Prinzmetal's angina: Perform cardiac evaluation in patients with cardiovascular risk factors. (5.1)
- Arrhythmias: Discontinue TREXIMET if occurs. (5.3)
- Chest/throat/neck/jaw pain, tightness, pressure, or heaviness: Generally not associated with myocardial ischemia; evaluate for coronary artery disease in patients at high risk. (5.4)
- Cerebral hemorrhage, subarachnoid hemorrhage, and stroke: Discontinue TREXIMET if occurs. (5.5)
- Gastrointestinal ischemic reactions and peripheral vasospastic reactions: Discontinue TREXIMET if occurs. (5.6)
- Hypertension: Monitor blood pressure. (5.7)
- Heart failure and edema: Use with caution in patients with fluid retention or heart failure. (5.8)
- Medication overuse headache: Detoxification may be necessary. (5.9)
- Serotonin syndrome: Discontinue TREXIMET if occurs. (5.10)
- Renal papillary necrosis and other renal injury with long-term use: Discontinue TREXIMET if occurs. (5.11)
- Anaphylactic reactions: TREXIMET should not be given to patients with the aspirin triad. (5.12)
- Serious skin reactions: Discontinue TREXIMET at first sign of rash. (5.13)

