4 CONTRAINDICATIONS

TREXIMET is contraindicated in the following patients:

- Ischemic coronary artery disease (CAD) (angina pectoris, history of myocardial infarction, or documented silent ischemia) or coronary artery vasospasm, including Prinzmetal's angina [see *Warnings and Precautions (5.1)*].
- History of coronary artery bypass graft (CABG) surgery [see *Warnings and Precautions (5.1)*].
- Wolff-Parkinson-White syndrome or arrhythmias associated with other cardiac accessory conduction pathway disorders [see *Warnings and Precautions (5.3)*].
- History of stroke or transient ischemic attack (TIA) or history of hemiplegic or basilar migraine because these patients are at a higher risk of stroke [see *Warnings and Precautions (5.5)*].
- Peripheral vascular disease [see *Warnings and Precautions (5.6)*].
- Ischemic bowel disease [see *Warnings and Precautions (5.6)*].
- Uncontrolled hypertension [see *Warnings and Precautions (5.7)*].
- Recent use (i.e., within 24 hours) of ergotamine-containing medication, ergot-type medication (such as dihydroergotamine or methysergide), or another 5-hydroxytryptamine₁ (5-HT₁) agonist [see *Drug Interactions (7.1, 7.3)*].
- Concurrent administration of a monoamine oxidase (MAO)-A inhibitor or recent (within 2 weeks) use of an MAO-A inhibitor [see *Drug Interactions (7.2), Clinical Pharmacology (12.3)*].
- Asthma, urticaria, or allergic-type reactions after taking aspirin or other NSAIDs [see *Warnings and Precautions (5.12, 5.13, 5.17)*].
- Hypersensitivity to sumatriptan, naproxen, or any other component of TREXIMET. Reactions have included angioedema and anaphylaxis [see *Warnings and Precautions (5.12)*].
- Third trimester of pregnancy [see *Warnings and Precautions (5.14), Use in Specific Populations (8.1)*].
- Severe hepatic impairment [see *Warnings and Precautions (5.15), Use in Specific Populations (8.7), Clinical Pharmacology (12.3)*].

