
Who should not take TREXIMET?**Do not take TREXIMET if you have:**

- heart problems, history of heart problems, or have ever had heart bypass surgery
- had a stroke, transient ischemic attack (TIAs), or problems with your blood circulation
- hemiplegic migraines or basilar migraines. If you are not sure if you have these types of migraines, ask your healthcare provider.
- narrowing of blood vessels to your legs and arms (peripheral vascular disease), stomach (ischemic bowel disease), or kidneys
- uncontrolled high blood pressure
- taken any medicines in the last 24 hours that are called 5-HT₁ agonists that are triptans or contain ergotamine. Ask your healthcare provider for a list of these medicines if you are not sure.
- taken an antidepressant medicine called a monoamine oxidase (MAO) inhibitor within the last 2 weeks. Ask your healthcare provider for a list if you are not sure.
- had an asthma attack, hives, or other allergic reaction with aspirin or any other NSAID medicine
- an allergy to sumatriptan, naproxen, or any of the ingredients in TREXIMET. See "What are the ingredients in TREXIMET?" below for a complete list of ingredients.
- third trimester of pregnancy
- liver problems

What should I tell my healthcare provider before taking TREXIMET?

Before you take TREXIMET, tell your healthcare provider about all of your medical conditions, including if you:

- have high blood pressure
- have high cholesterol
- have diabetes
- smoke
- are overweight
- have heart problems or a family history of heart problems or stroke
- have kidney problems
- have liver problems
- have had epilepsy or seizures
- are not using effective birth control
- are pregnant, think you might be pregnant, or are trying to become pregnant. **TREXIMET should not be used by pregnant women during the third trimester of their pregnancy.**
- are breastfeeding or plan to breastfeed. The components of TREXIMET pass into your breast milk and may harm your baby. Talk with your healthcare provider about the best way to feed your baby if you take TREXIMET.

Tell your healthcare provider about all the medicines you take, including prescription and over-the-counter medicines, vitamins, and herbal supplements.

TREXIMET and certain other medicines can affect each other, causing serious side effects.

How should I take TREXIMET?

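### The numbered eligibility criteria omit the no-contraindications condition of section 3.1, and three of the label's 13 contraindications are missing from 4.3 or only partly covered

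*Combined protocol and SAP*

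**What the plan says.** Section 3.1 (summary of study design) describes the population as triptan monotherapy users "who have no contraindications to triptan or NSAID use". Sections 4.2 and 4.3 then give 7 inclusion and 18 exclusion criteria. The lead-in to each list says that the listed items determine whether a subject is eligible. None of the 25 items is a general no-contraindication condition.

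Two exclusions deal with allergy:

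- Item 17 reads "subjects with allergy to naproxen".
- Item 18 bars aspirin or NSAID allergy "where such allergies induce syndrome of asthma, nasal polyps, urticaria and hypotension".

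The Treximet label is appended as 11.6. Its section 4 lists, among others:

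- "Asthma, urticaria, or allergic-type reactions after taking aspirin or other NSAIDs"
- "Hypersensitivity to sumatriptan, naproxen, or any other component of TREXIMET"
- "Wolff-Parkinson-White syndrome or arrhythmias associated with other cardiac accessory conduction pathway disorders"

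The Medication Guide in the same appendix tells patients not to take the drug if they "had an asthma attack, hives, or other allergic reaction with aspirin or any other NSAID medicine". The label Highlights word the NSAID item more narrowly: "Asthma, rhinitis, and nasal polyps syndrome induced by aspirin or other NSAID/analgesic drugs".

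The study flow chart in section 6 places the inclusion/exclusion check, randomization and drug dispensing together at Visit 1.

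**The concern.** The protocol states a safety condition in its design summary and then gives working criteria that do not carry it. Someone screening from 4.2 and 4.3 could enrol a patient for whom the study drug is contraindicated and still have followed every numbered item.

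The NSAID reaction is the gap that matters most. Subjects already take a triptan, so an unrecognised problem on the triptan side is less likely. Section 3.1, however, recruits patients whose migraine treatment contains no NSAID, so that treatment says nothing about whether they tolerate naproxen. Label sections 5.12 and 5.17 describe potentially fatal reactions in aspirin-sensitive patients.

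The next office visit after Visit 1 is Visit 5, after the first arm. For subjects who start on Treximet (30 planned under 4.1), Visit 1 is therefore the only scheduled eligibility check before dosing.

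**Working it through.** The plan gives no figure to reproduce here. The check maps each of the 13 items in label section 4 to the exclusions in 4.3.

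| Label section 4 item | Exclusion(s) in 4.3 | Coverage |
|---|---|---|
| Ischemic or vasospastic coronary disease | 8, 11 | Addressed |
| Coronary bypass surgery | 11 | Addressed |
| Stroke, TIA, hemiplegic or basilar migraine | 8, 11, 16 | Addressed |
| Peripheral vascular disease | 11 | Addressed |
| Ischemic bowel disease | 11 | Addressed |
| Uncontrolled hypertension | 12 | Addressed |
| Ergot or another 5-HT1 agonist within 24 hours | 14, 15 | Addressed |
| Third trimester of pregnancy | 7 | Addressed |
| Severe hepatic impairment | 10 | Addressed |
| MAO-A inhibitor, concurrent or within 2 weeks | 13 (no window stated) | Ambiguous |
| Reaction to aspirin or other NSAIDs | 18 | Partial |
| Hypersensitivity to a component | 17 | Partial |
| Accessory-pathway disorders | none | Absent |

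Count: 9 addressed + 1 ambiguous + 2 partial + 1 absent = 13. Absent or partial: 1 + 2 = 3.

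**NSAID reaction.** Item 18 joins four features with *and* as one syndrome. Label section 4 joins its terms with *or*, so any one reaction is enough, and the Medication Guide agrees. A patient whose only reaction was urticaria does not meet item 18 as written but is barred by the label. The Highlights also use a syndrome wording, so item 18 has a recognisable source. It does not match that source, however: it drops rhinitis and adds urticaria and hypotension.

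**Component hypersensitivity.** Item 17 names naproxen only. Sumatriptan is not covered, and the usual triptan need not be sumatriptan. The inactive ingredients are not covered either.

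**Accessory pathways.** No exclusion mentions them. Label section 5.3 repeats this contraindication next to its warning about life-threatening arrhythmias after 5-HT1 agonists.

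**Exposure.** Every subject is due Treximet in one of the two periods. With 500 mg naproxen sodium per tablet (section 5.1):

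- Initial doses only: 3 migraines × 1 tablet × 500 mg = 1,500 mg.
- At the limit of two tablets per migraine in 5.2: 3 × 2 × 500 mg = 3,000 mg. This is a permitted ceiling, because 5.3 describes a bottle of 3 tablets for the initial doses.

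These amounts describe planned exposure. They do not measure the risk of an allergic or cardiac event.

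**The case against.** The strongest reply is that the protocol already excludes nearly all of these patients. Section 3.1 is current text and the label is part of the protocol. Read together, they bar NSAID-induced urticaria and Wolff-Parkinson-White syndrome, and plausibly sumatriptan hypersensitivity. Only hypersensitivity to an inactive ingredient falls clearly outside 3.1. The flow-chart row for the eligibility check cites neither 4.2 nor 4.3, and a careful investigator taking a history at Visit 1 may well catch the rest. This lowers the risk. It does not repair the list, because 4.2 and 4.3 say that their items decide eligibility, and a row labelled inclusion/exclusion is naturally taken to mean those items.

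A second reply concerns consistency of reading. Item 15, taken literally, excludes users of 5-HT agonists and so every triptan user, which contradicts inclusion 6. The list must therefore be read for its purpose, and on such a reading item 18 could merely illustrate forms of NSAID allergy. That reading is possible. But item 18 is a restricting clause, and a safety exclusion should not depend on the screener choosing the generous interpretation.

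Other points stand in part:

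- The MAO-A item is weak. Item 13 refers to use without limit while item 14 specifies current use, which favours the wider reading. It is not counted among the three gaps.
- A migraine treatment without NSAIDs does not show that a patient has never taken one.
- A general label exclusion would by itself close the coverage gap and make the specific edits redundant for that purpose. They still help, because an uncorrected item 18 would sit in the same list as the general rule and point the screener to a narrower one.

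**Conclusion.** The concern holds. Three of the 13 label contraindications are absent from 4.3 (one) or only partly covered (two), and the general condition in 3.1 that would close most of the gap is not in the numbered criteria. The count becomes four if item 13 is read as current use only.

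This is a subject-safety and consistency defect in the eligibility text; estimates and power are unaffected. The number of patients concerned cannot be given, since the documents state no prevalence of NSAID reactions, accessory-pathway disorders or component hypersensitivity in this population. The conclusion rests on reading the numbered lists as the operative criteria, as their lead-ins say, and on taking the conjunction in item 18 at face value. The change should be made: it is cheap, and it aligns the list with the protocol's own stated condition and its own appendix.

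**What to change.** Five edits to section 4.3, with the clinical wording confirmed by the investigator:

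1. Add a numbered exclusion for any contraindication in section 4 of the current Treximet label. Note beside it that the 24-hour separation from another triptan applies at dosing and not at screening, since every subject is a triptan user.
2. Reword item 18 so that any one of asthma, hives or another allergic reaction following aspirin or an NSAID excludes the patient.
3. Add Wolff-Parkinson-White syndrome and arrhythmias due to other accessory-pathway disorders.
4. Extend item 17 to sumatriptan and every other tablet component, as well as naproxen.
5. State item 13 as current MAO-A inhibitor use or use in the preceding 2 weeks.

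The first two matter most; the fifth only removes an ambiguity. All five can be answered from the medical history and concomitant medications already collected at Visit 1, so no procedure is added. The cost is five lines of text and possibly a few more screen failures.
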